If one or both of the Dexcom G6 CGM's are more than 20 mg/dL different from the Reference Glucose Value for CGM values less than 100 mg/dL, or are more than 20% different from the Reference Glucose Value for CGM values greater than or equal to 100 mg/dL at any time during visit 3, they will be recalibrated against the result from the Reference Glucose Value (using the Dexcom G6 receiver(s)). This calibration must occur within 5 minutes of obtaining the Reference Glucose Value sample. If the Dexcom G6 Receivers are recalibrated, the matching mobile phone's Dexcom App must also be recalibrated at the same time (e.g., if Dexcom Receiver #1 is recalibrated, also recalibrate the Dexcom G6 Follow App in mobile phone #1). If a Dexcom G6 sensor is recalibrated, a follow up CGM one hour after the recalibration must be within 20 mg/dL of the Reference Glucose Value for CGM values less than 100 mg/dL, or within \pm 20% of the Reference Glucose Value for CGM values greater than or equal to 100 mg/dL. If a CGM is felt to be inaccurate – cannot be calibrated to meet the aforementioned CGM Validation Criteria – it may be replaced according to the CGM Replacement Criteria.
2. The Dexcom G6 CGM's are greater than 20% different than their averaged value. If the averaged glucose value of the two Dexcom G6 CGM's is greater than 20% different than the CGM values, a Reference Glucose Value will be obtained and both CGM's will be re-calibrated against the result of the Reference Glucose Value using the Dexcom G6 receivers. This recalibration must occur within 5 minutes of obtaining the Reference Glucose Value sample. In this scenario, the FUSION system will automatically alert the clinical study staff of the need to recalibrate both Dexcom G6 CGM's. If the Dexcom G6 Receivers are recalibrated, the matching mobile phone's Dexcom Follow Apps must also be recalibrated at the same time. If a Dexcom G6 CGM is recalibrated, the CGM value one hour after recalibration must be within 20 mg/dL of the Reference Glucose Value for CGM values less than 100 mg/dL, or within \pm 20% of the Reference Glucose Value for CGM values greater than or equal to 100 mg/dL.

DEMONSTRATION OF AN ARTIFICIAL INTELLIGENCE BASED CLOSED LOOP GLUCOSE CONTROL SYSTEM AS A THERAPEUTIC MODALITY IN TYPE 1 AND TYPE 2 DIABETIC PATIENTS

Protocol IMT 2022-1

CONFIDENTIAL

Version1.0.7

22 August 2022

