Prior to starting the closed loop glucose control session, a Reference Glucose Value will be obtained immediately after the time when the CGM sensors begin to return glucose readings. Reference Glucose Values will be subsequently checked every 30 minutes until the CGM sensor values meet the following CGM Validation Criteria:

1. CGM's must be within 20 mg/dL of the Reference Glucose Value for CGM values less than 100 mg/dL, or within \pm 20% of the Reference Glucose Value for CGM values greater than or equal to 100 mg/dL.

Closed-loop therapy will begin after two consecutive averages of CGM values meet the above CGM Validation Criteria. The above CGM Validation Criteria will be used throughout the entirety of visit 3.

Blood for independent glucose analysis will be drawn from the retrograde venous line in the warmed hand. The drawn blood will be immediately analyzed for glucose using the Nova StatStrip Hospital Glucose Meter System. These blood glucose values will be known as the Reference Glucose Values. If the arterialized venous line stops working, it may be replaced. If an arterialized venous line is no longer available, fingerstick capillary blood may be used for Reference Glucose Values. Fingerstick capillary blood will be analyzed using the Nova StatStrip Hospital Glucose Meter System.

All Reference Glucose Values will be manually recorded on the studies case report form, however, they will not be used by the FUSION system for purposes of glucose control (except to calibrate the Dexcom G6 CGM's, as necessary).

All subjects will be allowed to drink water throughout the course of the study. No glucose containing drinks will be allowed during the closed loop portion of the study, unless the subjects glucose level (CGM or Reference Glucose Value) is < 70 mg/dL, or the subject is experiencing symptoms of neuroglycopenia. Subjects will remain confined to either the bed or a bedside chair throughout the course of the study. Subjects will use a bedside commode for bathroom breaks in order to prevent any interruption to their closed loop glucose control session.

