8.1.1.5 VISIT 3, TIME 5 TO 29 HOURS (CLOSED LOOP GLUCOSE CONTROL SESSION)

The closed loop glucose control session will not begin until the following criteria has been met:

1. Both Dexcom G6 CGM's are returning glucose values and have been calibrated – if necessary; or replaced – if necessary.

Please refer to the below standard operating procedure (SOP) document for the calibration procedure for the Dexcom G6 CGM's, setting up the FUSION system, and initiating it's software:

FUSION System SOP

To better simulate how the FUSION system will be used in the ICU setting, no run-in period will be performed prior to the subject consuming the first meal. During the 24-hour closed loop glucose control study (time 5 to 29 hours), blood glucose control will be performed autonomously by Ideal Medical Technologies FUSION glucose control system. For safety reasons, the subjects will have a Reference Glucose Value independently measured every 10-60 minutes on the Nova StatStrip Hospital Glucose Meter System. These independent Reference Glucose Values will not be used by the FUSION system for glucose control. After 2-3 hours of confirmed CGM accuracy (e.g., from 0900 to 1200), the closed loop glucose control session will begin. The first meal consumed during the closed loop glucose control session will be lunch.

Lunch will consist of 60 grams of carbohydrate (45-60% of total meal Kcal's) and be consumed beginning at ~1200 hours (the beginning of the closed loop glucose control session). Dinner will consist of 75 grams of carbohydrates (45-60% of total meal Kcal's) and be consumed beginning at 1800 hours (6 hours after beginning of closed loop glucose control session). Breakfast will consist of 50 grams of carbohydrate (45-60% of total meal Kcal's) and be consumed beginning at 0800 hours on day 2 of the closed loop session began (20 hours after the beginning of the closed loop glucose control session).

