| 15. | 
Obtain Reference Glucose Values using the Nova StatStrip Hospital Glucose Meter System every 10-60 minutes from time 4 to 32 hours according to the following guidelines:
 
A. Every 10 minutes: Monitor the subject's Reference Glucose Values every 10 minutes whenever either of the following occur:
 
I. Either of the Dexcom G6 CGM's is less than 70 mg/dL.II. When the most recent Reference Glucose Value is less than 70 mg/dL. 
Discontinue every 10 minute Reference Glucose Value monitoring when both of the following have occurred:
 
I. Both Dexcom G6 CGM's are greater than 70 mg/dL.II. The subjects have two consecutive Reference Glucose Values greater than 70 mg/dL. These Reference Glucose Values will be measured by the Nova StatStrip Hospital Glucose Meter System on either a venous or capillary blood sample. 
B. Every 30 minutes: Monitor the subject's Reference Glucose Values every 30 minutes when the following occur:
 
I. After both Dexcom G6 CGM's begin to return glucose readings after their original insertion and prior to the onset of the closed loop glucose control session, for purposes of verifying the accuracy of the CGM's. This monitoring prior to the onset of the closed loop glucose control session may be discontinued once both CGM's have met the following CGM Validation Criteria on two consecutive Reference Glucose Values: 
CGM readings must be within ± 20 mg/dL of the Reference Glucose Value for CGM readings < 100 mg/dL or CGM readings must be within $\pm 20\%$ of Reference Glucose Values for CGM readings ≥ 100 mg/dL on two consecutive Reference Glucose Values.
 
II. During the first 2 hours of the closed loop glucose control session (time 5-7 hours).III. When either Dexcom G6 CGM has a glucose reading less than 85 mg/dL displayed on either the Dexcom G6 Receiver or the Dexcom G6 Follow App.IV. During periods of severe hyperglycemia, which is defined as a CGM or Reference Glucose Value greater than 240 mg/dL.V. When only one Dexcom G6 CGM is available for use by the FUSION system for glucose control.VI. After a CGM has been replaced, and until the replaced CGM has met the above noted CGM Validation Criteria.VII. When the subject experiences any signs of neuroglycopenia, regardless of the glucose level displayed by the CGM's.VIII. From time 29-32 hours, which is the 3 hour time period after conclusion of the closed loop glucose control session. |

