|-----|---|

| | |
|-----|--|
| | 
C. Every 60 minutes: Monitor the subject's Reference Glucose Value every 60 minutes when the following occur:
 
During the last 22 hours of the closed loop glucose control session (time 7-29 hours), if the following occur:
Both CGM's are in the range of 85-240 mg/dL and the subject is not experiencing any signs of neuroglycopenia. 
Result: _____ mg/dL, Time: _____ (24 hour clock) Note: Notify study team if the CGM or Reference Glucose Value is < 70 mg/dL or > 300 mg/dL.
 |
| 16. | 
Dexcom G6 CGM Placement, Calibration and Replacement
 
Visit 3 (Time 0 to 5 hours): Place two Dexcom G6 CGM's in the abdomen 5 cm to the right and left of the umbilicus (Figure 28).
  
18 years and older
 
Figure 28 – Green shaded areas denote appropriate areas of the abdominal wall to place the Dexcom G6 CGM's. This figure is from the Dexcom G6 CGM user manual.
 |

Make sure the Dexcom G6 Transmitters are labeled “#1” and “#2”. These labels should be in a clearly visible position after the Transmitters have been attached to the Dexcom G6 glucose sensors. Once both Dexcom CGM’s begin to return glucose values, obtain a Reference Glucose Value using the Nova StatStrip Hospital Glucose Meter System. If either of the Dexcom CGM’s do not meet CGM Validation Criteria, they may be calibrated. The Dexcom G6 CGM’s must meet the following CGM Validation Criteria throughout the CRC study session (visit 3), otherwise they will be calibrated as often as is necessary:

1. CGM readings must be within ± 20 mg/dL of the Reference Glucose Value for CGM readings < 100 mg/dL or CGM readings must be within $\pm 20\%$ of Reference Glucose Values for CGM readings ≥ 100 mg/dL on two consecutive Reference Glucose Values.

Calibrations should only be attempted when the glucose rate of change is less than ± 2 mg/dL/min on the Dexcom G6 CGM (see figure 29).

If after two calibration attempts prior to beginning the closed loop glucose control session (time 0-5 hours) the CGM(s) still do not meet CGM Validation Criteria, they may be replaced. The closed loop glucose control session may not begin until there are two working Dexcom G6 CGM’s in place, and both CGM’s have met the above noted CGM Validation Criteria.

Closed Loop Glucose Control Session (Time 5 to 29 hours):

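### Section 8.1.1.4 lets closed loop start on two passing averages of the CGMs, Protocol 2 requires each CGM to pass, and nothing says which rule governs

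*Combined protocol and SAP*

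**What the plan says.** Four current passages bear on when the loop may start.

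- **Section 8.1.1.4, item 6.** The pre-start checks are described per sensor: "Reference Glucose Values will be subsequently checked every 30 minutes until the CGM sensor values meet the following CGM Validation Criteria". The sentence that permits the start then turns to the average: "Closed-loop therapy will begin after two consecutive averages of CGM values meet the above CGM Validation Criteria".
- **Protocol 2, item 16.** "The closed loop glucose control session may not begin until there are two working Dexcom G6" sensors in place, and both "have met the above noted CGM Validation Criteria".
- **Protocol 2, item 15.B.I.** "This monitoring prior to the onset of the closed loop glucose control session may be discontinued once both" sensors have passed on two consecutive Reference values.
- **Section 8.1.1.5.** The numbered condition asks only that both sensors "are returning glucose values and have been calibrated" or replaced, in each case if necessary. The text below it expects 2-3 hours of confirmed accuracy, for example 0900 to 1200, without saying whether that means each sensor or their average.

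Section 8.1.1.4, item 6, also governs a single sensor that fails against the Reference. It must be recalibrated, and "This calibration must occur within 5 minutes of obtaining the Reference Glucose Value sample". After that, "a follow up CGM one hour after the recalibration must be within 20 mg/dL of the Reference Glucose Value" (or within 20% at CGM values of 100 mg/dL and above). Nothing in that rule makes the start wait for the follow-up.

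**The concern.** An average can pass while one of its two components fails. The FUSION discrepancy alarm does not close the gap, because it compares each sensor with the average and not with the Reference. A nurse working from section 8 could therefore start the loop in a state that Protocol 2 prohibits.

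At stake is redundancy. Section 4.3.1 relies on two sensors as the mitigation for sensor failure and lets FUSION run on one for up to four hours. A per-sensor gate establishes that either sensor could be trusted alone; an average gate does not. The device gives intravenous insulin autonomously, so its start condition should have one reading.

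**Working it through.** **Inputs**

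- Control value: A = (C1 + C2)/2 (section 4.3.1).
- Validation against Reference R: |C − R| ≤ 20 mg/dL if C < 100; |C − R| ≤ 0.20 × R if C ≥ 100 (section 8.1.1.4, item 6).
- Discrepancy alarm: |Ci − A|/A > 20% (section 8.1.1.4, item 6; Protocol 2, item 17).

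**Step 1: reproduce the plan's alarm example.** Item 17 uses CGMs of 70 and 130. A = (70 + 130)/2 = 100, and 30/100 = 30% > 20%, so the alarm sounds, as stated.

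**Step 2: pairs that pass on the average, raise no alarm and contain a failing sensor.**

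| R | CGMs | A | A vs R | CGM vs A | Failing sensor vs R |
|---|---|---|---|---|---|
| 110 | 110, 150 | 130 | 20/110 = +18.2%, pass | 20/130 = 15.4%, silent | 40/110 = +36.4% |
| 150 | 150, 105 | 127.5 | −22.5/150 = −15.0%, pass | 22.5/127.5 = 17.6%, silent | −45/150 = −30.0% |

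Section 8.1.1.4 counts either check towards the start; Protocol 2, item 16, does not.

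**Step 3: the limit.** Where the 20% rule applies, the average can reach 1.2R or 0.8R, and a sensor can lie 20% beyond it without an alarm. 1.2 × 1.2 = 1.44 and 0.8 × 0.8 = 0.64, so one sensor can be 44% high or 36% low. At R = 150 these are the pairs 216/144 (A = 180) and 96/144 (A = 120).

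**Step 4: order of events.** Suppose a sensor fails at minute 0 behind a passing average and is recalibrated. The average passes again at minute 30. Two consecutive averages have now passed and the section 8.1.1.4 sentence is satisfied, but the one-hour follow-up is not due until about minute 60. Under Protocol 2 the earliest two consecutive passes for that sensor are at minutes 30 and 60, so the second coincides with the follow-up.

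**Step 5: what the per-sensor gate would delay.** The documents give no G6 error size, so these inputs are assumptions: two independent sensors; unbiased normal percentage errors with SD 9%, 11.4% or 15%; Reference 120-200 mg/dL; checks every 30 minutes from 0900. A failing sensor has its error reset to zero and then drifts. The gate is both sensors passing two consecutive checks, with any recalibrated sensor re-verified at least one hour later. The middle SD is the 9.1% abdominal MARD in section 4.3.3 divided by 0.798; that MARD is for the G7.

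| Gate not yet met | Correlation 0.8: SD 9% / 11.4% / 15% | Correlation 0.5: highest, at SD 15% |
|---|---|---|
| by 1200 | about 0.002% / 0.04% / 0.7% | about 4% |
| by 1100 | about 0.06% / 0.6% / 3.7% | about 12% |

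For eight subjects at 1200, the largest figures are 8 × 0.007 = 0.06 and 8 × 0.04 = 0.3 of a subject.

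**The case against.** The strongest reply is that the stricter rule already exists and can be obeyed together with the looser one. Item 16 is a flat prohibition, section 8.1.1.7 sends staff to Protocol 2 for the meal challenge, and section 8.1.1.4 itself words the criteria per sensor just before the averages sentence. Staff who apply item 16 are protected. That stands as a limit on the risk. It does not settle the text: no order of precedence is given, the averages sentence is directive, and following it can breach item 16.

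Two stronger readings are tempting and not supported.

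- A reader might infer that a bad sensor goes unnoticed. It should not. The Reference value that validates the average also exposes the failing sensor, and recalibration is then required; only the FUSION alarm is silent.
- A reader might simulate a start at the second 30-minute check and conclude that many subjects would start with an unverified sensor, or be delayed by a stricter gate. Section 8.1.1.5 and Protocol 2 (items 8 and 19) plan the start for about 1200, with 2-3 hours of checking beforehand. A sensor recalibrated at 0900 is due its follow-up at about 1000.

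The harm path is also narrow: the accurate sensor must drop out before the other is corrected. In the first example FUSION would then act on 150, above its 100-140 range, at a Reference of 110, and the remaining CGM would not be below the 85 mg/dL trigger. Reference checks every 30 minutes apply in the first two hours and whenever only one CGM is available (Protocol 2, item 15.B).

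**Conclusion.** The conflict is real and lies in current text: one section gates the start on the average, another on each sensor, and a third on neither explicitly. Taken literally, section 8.1.1.4 permits a start with one sensor up to 44% high or 36% low where the 20% rule applies, or recalibrated and not re-verified. That part is arithmetic and needs no assumption about sensor performance.

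The consequence is modest. The controller's averaged input is in tolerance at the start, so the exposure is a short period without verified redundancy, not a wrong input at time 0. A reader might infer bias in the primary endpoints; nothing here shows it, and none is claimed. How often such a start would occur cannot be settled from the documents. The FUSION System SOP cited in section 8.1.1.5 was not available and may add a gate. The change should still be made, because the start rule of an autonomous insulin device ought to be single and unambiguous.

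**What to change.** Replace the averages sentence in section 8.1.1.4, item 6, with:

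> *Closed-loop therapy will begin after each CGM individually meets the CGM Validation Criteria on two consecutive Reference Glucose Values, and any recalibrated or replaced CGM has been re-verified.*

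Cross-refer to this rule in the section 8.1.1.5 start condition, and check that the FUSION System SOP agrees.

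The text cost is one sentence and one cross-reference. The operational cost is an occasional start after 1200, which is rare under the assumptions in the working. It becomes more likely if the sensors begin reading late: with only two hours of checking, the highest figure is about 12% (8 × 0.12 = about 1 of 8 subjects, at SD 15% and correlation 0.5). The re-verification clause adds little, since two consecutive passes at 30-minute intervals after a recalibration already take an hour.

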8.1.1.5 VISIT 3, TIME 5 TO 29 HOURS (CLOSED LOOP GLUCOSE CONTROL SESSION)

The closed loop glucose control session will not begin until the following criteria has been met:

1. Both Dexcom G6 CGM's are returning glucose values and have been calibrated – if necessary; or replaced – if necessary.

Please refer to the below standard operating procedure (SOP) document for the calibration procedure for the Dexcom G6 CGM's, setting up the FUSION system, and initiating it's software:

FUSION System SOP

To better simulate how the FUSION system will be used in the ICU setting, no run-in period will be performed prior to the subject consuming the first meal. During the 24-hour closed loop glucose control study (time 5 to 29 hours), blood glucose control will be performed autonomously by Ideal Medical Technologies FUSION glucose control system. For safety reasons, the subjects will have a Reference Glucose Value independently measured every 10-60 minutes on the Nova StatStrip Hospital Glucose Meter System. These independent Reference Glucose Values will not be used by the FUSION system for glucose control. After 2-3 hours of confirmed CGM accuracy (e.g., from 0900 to 1200), the closed loop glucose control session will begin. The first meal consumed during the closed loop glucose control session will be lunch.

Lunch will consist of 60 grams of carbohydrate (45-60% of total meal Kcal's) and be consumed beginning at ~1200 hours (the beginning of the closed loop glucose control session). Dinner will consist of 75 grams of carbohydrates (45-60% of total meal Kcal's) and be consumed beginning at 1800 hours (6 hours after beginning of closed loop glucose control session). Breakfast will consist of 50 grams of carbohydrate (45-60% of total meal Kcal's) and be consumed beginning at 0800 hours on day 2 of the closed loop session began (20 hours after the beginning of the closed loop glucose control session).

Subjects will be allowed to have snacks between the hours of 2100 on day 1 and 0600 hours on day 2 of their CRC study, or at any time for CGM or Reference Glucose Values less than 70 mg/dL or for symptoms of neuroglycopenia. Subjects will preselect their breakfast, lunch, and dinner meal choices from the CRC menu prior to the study. These meals will be unannounced to the FUSION system. Once the closed loop glucose control period has ended after 24 hours of glucose control, the control software will be stopped, and the subject will be disconnected from all intravenous infusions.

If the subjects are removed from the study due to the occurrence of a severe hypoglycemic event (< 54 mg/dL), the subjects will have their glucose values measured with a Reference Glucose Analyzer (e.g., Nova StatStrip Hospital Glucose Meter System) every 10 minutes, until their Reference Glucose Values are greater than 70 mg/dL. They will then have additional Reference Glucose Values drawn every 30 minutes, until they have consistent Reference Glucose Values in the range of 80-250 mg/dL for a period of at least two hours. See *Recovery Period* (Pages 107-108) for details with regards to subcutaneous insulin doses to be received prior to discharge from the Clinical Research Center.

The insulin and dextrose 50 mL medication syringes may not be used for more than 24 hours. Although the study should be terminated after a period of 24 hours (e.g., may not go longer than 24 hours), if for any reason the study period is longer than 24 hours (e.g., on orders from the principal investigator), the insulin and dextrose medication syringes must be exchanged for new medication syringes. To be clear, the insulin and dextrose medication syringes may not be used for a period of time exceeding 24 hours.

8.1.1.6 VISIT 3, TIME 29 TO 32 HOURS (OBSERVATION AFTER CLOSED LOOP GLUCOSE CONTROL SESSION)

At the end of the subjects 24 hour closed loop glucose control session, they will be fed lunch consisting of 60 grams of carbohydrate (45-60% of total meal Kcal's). The subjects will resume control of their blood glucose per the protocol instructions (see IMT2022-1-P2) once the closed loop glucose control period has ended. After finishing their lunch, the subjects will continue to have Reference Glucose Values measured every 30 minutes using the Nova StatStrip Hospital Glucose Meter System. When the subjects Reference Glucose Value is in the range of 80-250 mg/dL for a period of at least two hours after the end of their closed loop glucose control session and their most recent glucose rate of change is less than ± 2 mg/dL/min, their intravenous catheters will be removed, and they will be discharged from the CRC. If their blood Reference Glucose Value is less than 80 mg/dL, they will be given additional snacks until their Reference Glucose Value is greater than 80 mg/dL. If the subjects require additional snacks, they will continue to have Reference Glucose Values measured every 30 minutes using the Nova StatStrip Hospital Glucose Meter System until their Reference Glucose Value has been stable in the range of 80-250 mg/dL on four consecutive values and their most recent glucose rate of change is less than ± 2 mg/dL/min, after which time their intravenous catheters will be removed, and they will be discharged from the CRC unit. If their Reference Glucose Value is greater than 250 mg/dL the study's principal investigators ([name] or [name]) will order a dose of short acting insulin, which will be administered by the clinical study nurse, and their Reference Glucose Value will be monitored every 30 minutes until it is less than 250 mg/dL and their most recent glucose rate of change is less than ± 2 mg/dL/min, at which time they may be discharged from the CRC unit.

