| | 
Both type 1 and type 2 diabetic subjects will consume a lunch consisting of 60 grams of carbohydrates beginning at 1200 hours on day 2.
 
The study nurse will check Reference Glucose Values every 30 minutes with the Nova StatStrip Hospital Glucose Meter System – Times 29, 29.5, 30, 30.5, 31, 31.5, and 32 hours, etc., until the subjects Reference Glucose Values are in the range of 80-250 mg/dL for a period of at least two hours after the completion of the closed loop glucose control session, and the most recent glucose rate of change is less than \pm 2 mg/dL/min.
 
If the subject is removed from the study early due to the presence of hypoglycemia (e.g., < 54 mg/dL or < 70 mg/dL with neuroglycopenic symptoms) or for any other reason, they will have ongoing monitoring in the CRC until they have had glucose values in the range of 80-250 mg/dL for a period of at least two hours, and until their most recent glucose rate of change is less than \pm 2 mg/dL/min. In the event the subject is removed from the study early, any short or long acting insulin dosing needed from the time the subject is removed from the study until the time the subject is discharged from the CRC, will be per the orders of the study's principal investigators ([name] or [name]).
 
If the subjects CGM or Reference Glucose Values are less than 70 mg/dL at the time they are removed from the study, they will have Reference Glucose Values measured every 10 minutes until such time as their glucose values are greater than 70 mg/dL. If the subject develops signs of diabetic ketoacidosis (e.g., Reference Glucose Value > 240 mg/dL and blood ketones > 1 mmol/L), they will have a basic metabolic panel, venous pH, and beta hydroxybutyrate drawn. If the subject develops diabetic ketoacidosis, they will be stabilized and have ongoing care per the usual routine of Emory Healthcare.
 |
| 21. | 
Intravenous Catheter Removal:
 
Remove both IV catheters once the subjects Reference Glucose Value is in the range of 80-250 mg/dL for a period of at least two hours after the completion of the closed loop glucose control session, and when the most recent glucose rate of change is less than \pm 2 mg/dL/min. This criterion will not be met prior to time 32 hours (\sim 1500 hours of 2nd day in the CRC). The subject may be discharged from the CRC unit once this criterion has been met.
 |

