| 22. | 
Discharge Criteria
 
The subjects Reference Glucose Value must be between 80-250 mg/dL for a period of 2 hours before discharge, and their most recent glucose rate of change must be less than \pm 2 mg/dL/min. For subjects who have been placed back on their usual continuous subcutaneous insulin infusion pump, they may be discharged once their Reference Glucose Value is between 80-250 mg/dL for a period of 2 hours, and their most recent glucose rate of change must be less than \pm 2 mg/dL/min.
 |

DEMONSTRATION OF AN ARTIFICIAL INTELLIGENCE BASED CLOSED LOOP GLUCOSE CONTROL SYSTEM AS A THERAPEUTIC MODALITY IN TYPE 1 AND TYPE 2 DIABETIC PATIENTS

Protocol IMT 2022-1

CONFIDENTIAL

Version1.0.7

22 August 2022

| | |
|------------|--|
| | 
All subjects must be observed for a minimum of 3 hours after the conclusion of the closed loop glucose control session and for at least 60 minutes after their most recent subcutaneous insulin injection (subjects on MDI insulin therapy), before being discharged from the CRC.
 
End of Study Reference Glucose Value, BG: _____ mg/dL, Time: _____ (24 hour clock)
 |
| 23. | 
After the subjects have been discharged from the CRC, they will be instructed to check their blood glucose levels at home using their blood glucose meter at the following times:
 
1. On arrival at home.2. Before dinner.3. At 9 P.M.4. On awakening the next morning. 
Subject to call study coordinator with concerns they have about their glucose levels or any other issue.
 |

Attachment 1

Serious Adverse Event Report Form

IMT2022-1-A1

Serious Adverse Event

An adverse event is any untoward medical event associated with use of a drug or drug delivery system in humans, whether or not it is considered related to a drug or drug delivery system. For purposes of this study, a Serious Adverse Event (SAE) is any adverse event from this study that results in one of the following outcomes:

- Death
- A life threatening experience
- Persistent or significant disability/incapacity
- Seizure secondary to hypoglycemia
- Myocardial infarction that is temporally related to a hypoglycemic (<70 mg/dL) event
- Cardiac dysrhythmia that is temporally related to a hypoglycemic (<70 mg/dL) event
- Any other complication related to hypoglycemia
- Reference Glucose Value less than 54 mg/dL
- Considered significant for any other reason

Serious Adverse Event (SAE) Report Form

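### Section 8.1.1.6 sets looser discharge rules than Protocol 2 item 22, most clearly after corrective insulin, where one 30-minute value below 250 mg/dL is enough

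*Combined protocol and SAP*

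**What the plan says.** Section 8.1.1.6 (Visit 3, time 29 to 32 hours) has three routes to discharge, each with a rate-of-change limit of ±2 mg/dL/min.

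- **Ordinary branch.** The value must be "in the range of 80-250 mg/dL for a period of at least two hours after the end of their closed loop glucose control session". The intravenous catheters then come out and the subject leaves.
- **Snack branch**, after a value below 80 mg/dL. The value must be "stable in the range of 80-250 mg/dL on four consecutive values", after which the catheters come out and the subject leaves.
- **Corrective insulin branch**, after a value above 250 mg/dL. A principal investigator orders short acting insulin and the nurse gives it. The value is "monitored every 30 minutes until it is less than 250 mg/dL and their most recent glucose rate of change is less than" the limit, "at which time they may be discharged from the CRC unit". Catheters are not mentioned.

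Protocol 2 (IMT2022-1-P2) is stricter. Item 22 says: "The subjects Reference Glucose Value must be between 80-250 mg/dL for a period of 2 hours before discharge", with the same rate limit. It adds: "All subjects must be observed for a minimum of 3 hours after the conclusion of the closed loop glucose control session", and MDI subjects must also wait 60 minutes after their latest subcutaneous injection. It makes no exception for corrective insulin. Item 21 ties catheter removal to two hours in range and adds: "This criterion will not be met prior to time 32 hours". Item 20 asks for four consecutive values in 80-250 mg/dL in both diabetes types, and also for two hours in range after the session.

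Section 10.1 item 7 refers discharge to the Protocol 2 criteria.

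**The concern.** Within Section 8.1.1.6 the shortest rule applies to the subjects who have just received extra insulin. A subject who never left the range must hold it for two hours, and one who needed a snack must show four values. A subject treated for a value above 250 mg/dL needs one value below that limit. The corrective dose comes on top of the lunch dose and, depending on regimen, basal or long acting insulin or a restarted pump (Protocol 2 item 20). No reason is given for the shorter rule.

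Staff working from Section 8.1.1.6 could therefore release a subject while the corrective dose is still acting. Half-hourly Reference values with staff present would be replaced by the home meter checks of Protocol 2 item 23 and a call to the coordinator if the subject is worried. What is at stake is subject safety in the hours after the session.

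**Working it through.** The plan gives no figure to reproduce. The check places both sets of rules on the same 30-minute grid.

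**Inputs**
- Session end: 29.0 h (Section 8.1.1.5 and Schedule of Activities).
- Reference values every 30 minutes (Section 8.1.1.6; item 20 lists the times from 29 h).
- Item 22: 3 hours of observation, so not before 29.0 + 3.0 = 32.0 h; 2 hours in range; 60 minutes after a subcutaneous injection for MDI subjects.
- Assumed readings: 260 mg/dL, insulin given at once, then 245 mg/dL 30 minutes later. The rate is (245 − 260)/30 = −0.5 mg/dL/min, inside the limit in both texts.
- Assumed route: subcutaneous. Section 8.1.1.6 does not state it. Only the 60-minute term depends on it.
- Assumed course: values stay in range afterwards.

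**Corrective insulin branch**, dose at time t (hours):
- Section 8.1.1.6: t + 0.5.
- Item 22: max(32.0, t + 1.0, t + 0.5 + 2.0).

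| Dose at | Section 8.1.1.6 | Item 22 | Gap |
|---|---|---|---|
| 31.5 h | 32.0 h | max(32.0, 32.5, 34.0) = 34.0 h | 120 min |
| 29.5 h | 30.0 h | max(32.0, 30.5, 32.0) = 32.0 h | 120 min |

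In the late case the time from dose to discharge is 30 minutes against 150. In the early case the subject could leave one hour after the session. For any dose at 29.5 h or later the two-hour term is at least 32.0 h, so the gap stays at 120 minutes. A dose triggered by the reading at 29.0 h would give 29.5 h against max(32.0, 30.0, 31.5) = 32.0 h, or 150 minutes. That reading precedes lunch and would naturally be handled in the lunch dose, so I take 29.5 h as the first realistic case.

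**Ordinary branch**
- Section 8.1.1.6: 29.0 + 2.0 = 31.0 h.
- Item 22: max(32.0, 31.0) = 32.0 h. Gap: 60 minutes.

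**Snack branch**, one value below 80 mg/dL at time s and in range from s + 0.5:
- Four values span 3 × 30 = 90 minutes, so Section 8.1.1.6 gives s + 0.5 + 1.5 = s + 2.0.
- Item 22: max(32.0, s + 2.5).
- s = 29.0: 31.0 h against 32.0 h, gap 60 minutes.
- s = 29.5: 31.5 h against 32.0 h, gap 30 minutes. It stays at 30 minutes for later s.

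**Does item 20's four-value rule clash with item 22?** Two hours in range on a 30-minute grid means 120/30 + 1 = 5 consecutive values, so meeting item 22 also meets item 20.

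**The case against.** The best reply is that the plan already settles the matter. Section 8.1.1.6 says these subjects may leave, whereas item 22 says what must be met, so staff who follow item 22 satisfy both texts. Section 10.1 item 7 sends discharge to Protocol 2. Protocol 2 is the step-by-step bedside document, with blanks for the insulin doses and the end-of-study glucose. The catheters are a practical brake: the corrective insulin branch gives no instruction to remove them, and item 21 keeps them in until two hours in range and not before 32 h. A principal investigator orders every dose, and subjects already use insulin at home.

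Most of this stands, and it limits the risk. It shows which rule is probably intended, but it does not withdraw the permission that Section 8.1.1.6 gives. That section's own pointer to Protocol 2 concerns resuming glucose control and says nothing of discharge. The 29-to-32-hour heading is not a minimum stay, and the late example breaks the two-hour rule even at 32.0 h.

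A reader might infer that the snack branch's four-value rule is foreign to Protocol 2. It is not, because item 20 states the same rule beside two hours in range. What the snack branch lacks is the two-hour and 3-hour requirements. A reader might also infer that every subject who leaves early must meet all of item 22. Section 9.3 does apply all the recovery-period discharge criteria to those who withdraw themselves, but for early removal item 20 states only the two-hour and rate rules.

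**Conclusion.** The point holds as an inconsistency in discharge rules that should be fixed. Section 8.1.1.6 is looser than item 22 on all three branches. The gap is about 2 hours after corrective insulin, 1 hour on the ordinary branch, and 30 to 60 minutes on the snack branch. These sizes rest on the 30-minute grid, illustrative glucose readings and values that stay in range. The two-hour conflict does not depend on the route of the corrective dose.

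A reader might infer that the corrective insulin branch is a lone dangerous exception, or that the plan compels early release. The documents support neither. Section 8.1.1.6 reads as a looser summary throughout, its wording on this branch is permissive, and Section 10.1 item 7 points to the stricter rule. Nor is any result at risk, because the endpoint time frame ends when the controller stops. Only those of the eight subjects who exceed 250 mg/dL after the session meet the corrective insulin branch, and the documents do not say how many to expect.

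**What to change.** In Section 8.1.1.6, delete the permission to discharge after corrective insulin and keep the 30-minute monitoring. Add one sentence stating that Protocol 2 item 22 governs discharge for all subjects on every branch, including those given corrective insulin or snacks. Protocol 2 items 20 to 22 can stay as they are.

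The cost is a wording amendment to one paragraph. Compared with the current Section 8.1.1.6, a subject may stay up to about 2 hours longer after corrective insulin and up to about 1 hour longer on the ordinary or snack branch. Where staff already work from item 22, nothing changes.
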